8.2 Determination of Sample Size and Accrual Rate

8.2.1 Sample Size and Power Estimate

The primary endpoint is to evaluate the sensitivity on a (1) per-patient and (2) per-region-basis (prostate bed, pelvis, extrapelvic soft tissue, and bone metastases) of ^{68}Ga -PSMA-11 PET for detection of tumor location confirmed by histopathology/biopsy. Based on our first protocol in biochemical recurrent patients, we have updated the distribution of disease that we expect to find:

- a) Prostate bed: 15%
- b) Pelvis: 27%
- c) Extrapelvic soft tissue: 24%
- d) Bone metastases: 11%
- e) No evidence of disease on PSMA PET: 24%

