Of our first cohort of patients, 19% of patients underwent biopsy after a positive PSMA PET imaging. Based on biopsy results there was 100% sensitivity and 87% specificity. There were no True Negatives or False Negatives on biopsy. Imaging follow-up is not complete for our first study so we cannot estimate the percent of patients that will have imaging follow-up, but it appears that roughly 15 to 20% of patients will have imaging follow-up. Consistent with our second protocol, we anticipated that the sensitivity for the four regions and for all regions combined using conventional imaging ranges from 30-60%. An overall sensitivity for ^{68}Ga -PSMA-11 PET of at most 50% will be considered as unacceptably low. Hence, the null hypothesis that the sensitivity is at most 50% will be tested against the alternative hypothesis that the sensitivity is greater than 50%. It is hypothesized that ^{68}Ga -PSMA-11 PET imaging on the per-region and per-patient basis will substantially increase the sensitivity for the four regions to at least 70%. A sample size of 75 true positives is required for rejecting the null hypothesis that the sensitivity is at most 50% with 90% power at the one-sided 0.01 ($=0.05/5$ – a Bonferroni adjustment for evaluating the sensitivity for the four regions and for all regions combined) significance level, assuming an average regions specific prevalence of 20%. Although 19% of patients underwent biopsy and 15% of patients have imaging follow-up, we anticipate that the biopsy rate will fall in this study as referring clinicians become more comfortable with the imaging results. Therefore, we will combine imaging and biopsy follow-up in the primary aim, and will require 375 with both imaging and/or biopsy follow-up in order to power the analysis at a per region level. Assuming a prevalence rate of 20% for disease in each individual region, a total sample size of 1,500 patients is required. In summary, the proposed target accrual of 1,500 patients (375 with biopsies or imaging follow-up) will provide adequate power for detecting the anticipated improvement in the sensitivity for both the per-patient and per-region based ^{68}Ga -PSMA-11 PET imaging. However, a sample size of 107 patients with biopsies/follow-up in total is sufficient for detecting the anticipated improvement in sensitivity when evaluating per-patient based sensitivity.

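### Sections 8.2.1 and 8.2.2 contradict themselves: stated accrual gives 500 patients, not 1,500, and the 375 verified patients assume 20% prevalence in every region although 11% is expected for bone

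*Combined protocol and SAP*

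**What the plan says.** Section 8.2.1 tests sensitivity of at most 50% against 70%, at one-sided 0.01 (0.05/5, for four regions and all regions combined) with 90% power. It states that "A sample size of 75 true positives is required", first "assuming an average regions specific prevalence of 20"% and then more strictly: "Assuming a prevalence rate of 20% for disease in each individual region, a total sample size of 1,500 patients is required". It asks for 375 verified patients to power the regional analysis, and adds that for the per-patient analysis "a sample size of 107 patients with biopsies/follow-up in total is sufficient". It concludes that the target accrual "will provide adequate power for detecting the anticipated improvement in the sensitivity for both the per-patient and per-region based" imaging.

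The distribution of disease listed in the same section is not uniform: "Prostate bed: 15"%, pelvis 27%, extrapelvic soft tissue 24%, "Bone metastases: 11"%, and no evidence of disease on PET 24%. On verification in the earlier cohort, it reports that "19% of patients underwent biopsy after a positive PSMA PET imaging".

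The abstract, section 3.2 and section 8.2.1 all give 1,500 patients. Section 8.2.2 gives about 250 a year in this trial and up to 500 over two years. Primary completion is at 36 months (3.5.1). Study completion is at three years in the abstract and at 48 months in 3.5.2.

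**The concern.** Per-region power is the only reason the plan gives for 375 verified patients (1,500 enrolled) rather than 107 verified. That reason needs every region to supply about 75 diseased cases. An average prevalence of 20% cannot secure this in the rarest region, and each region has its own share of the Bonferroni adjustment. Separately, if enrolment follows section 8.2.2, the trial ends with a third of the patients on which the power statement rests. Regional sensitivity is part of the primary objective, so a reader would take the power claim at face value.

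**Working it through.** **1. The plan's own figure.** One-sample binomial test, p0 = 0.50, p1 = 0.70, one-sided 0.01:

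n = ((2.326 × 0.5 + 1.282 × √0.21) / 0.2)² = 76.6.

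At n = 75, power is 84.3% exact and 89.3% by the normal approximation, so 75 reproduces to within two cases. Then 75/0.20 = 375, 375/1,500 = 25% implied verification, and 75/0.70 = 107. Since 75/0.20 divides by prevalence alone, 75 is being used as a count of diseased units; 75 literal true positives would need 75/(0.70 × 0.20) = 536 verified patients.

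**2. The 20% input.** The four regional shares average (15 + 27 + 24 + 11)/4 = 19.25%, so 20% fits only as a mean. All five entries sum to 101%, which suggests one category per patient.

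**3. Bone at 375 verified.** The plan does not say how a share becomes a number of diseased verified cases. Four conversions are possible (0.76 = 1 − 0.24):

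| Conversion | Bone cases | Power, exact / normal |
|---|---|---|
| Share = prevalence among verified: 375 × 0.11 = 41.25 | 41 (42) | 54% / 60% (63% / 61%) |
| Only PET-positive patients verified: 41.25/0.76 = 54.3 | 54 | 76% / 75% |
| Share is a PET-positive rate, divided by 70% sensitivity: 41.25/0.70 = 58.9 | 59 | 79% / 79% |
| Both adjustments: 41.25/(0.76 × 0.70) = 77.5 | 77–78 | 86–90% / 90–91% |

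The last two rows ignore false positives. Exact power is stepped, so neighbouring counts can differ by several points. The expected 95% Wilson interval at an observed 70% is 55–82% with 41 cases and 57–81% with 54.

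**4. Other regions at 375.** Prostate bed has 56 cases (69% / 77%) under the first conversion and 74 (86% / 89%) under the second; the second matches the n = 75 design. Extrapelvic tissue (90 cases, 93% / 95%) and pelvis (101 cases, 96% / 97%) exceed 90% even under the first.

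**5. Accrual.** 250 × 2 = 500; 250 × 3 = 750; 250 × 4 = 1,000; 1,500/250 = 6 years. No stated timeline reaches 1,500.

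**6. Power at 500 enrolled.** With 25% verified, 500 × 0.25 = 125. Bone has 125 × 0.11 = 13.75 to 13.75/(0.76 × 0.70) = 25.8 cases. Power is 16% / 18% at 14 cases and 30% / 38% at 26. The best-placed region under the most favourable conversion is pelvis: 125 × 0.27/(0.76 × 0.70) = 63.4 cases, 77% / 82% at 63. For the per-patient test, assuming 70% of verified patients are diseased, 125 × 0.70 = 87.5; 88 cases give 92% / 94%.

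**The case against.** The strongest reply concerns the meaning of the shares. The list ends with PET-negative patients, so the entries look like PET findings rather than true prevalence. If the true sensitivity is 70%, diseased cases exceed PET-positive cases, and with verification confined to PET-positive patients bone has 77 or 78 cases, as good as the plan's n = 75. This stands. A reader might infer that bone misses 90% power however the plan is read; the documents do not support that.

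Other points in the plan's favour also stand in part. If patients can have disease in several regions, 11% is a minimum. Bone may be verified more often than other sites, because 8.3.2 accepts baseline CT, bone scan or MRI. The plan gives a figure for neither. The alternative is at least 70%; at 80%, 41 cases would give 95% exact power, but the 90% claim was sized at 70%.

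The 25% verification rate is implied, not stated. Section 8.2.1 reports 19% biopsy and 15–20% imaging follow-up, or 34–39% without overlap, although it expects biopsies to fall. At 500 enrolled, 39% would give 195 verified and at most 195 × 0.11/(0.76 × 0.70) = 40 bone cases, 58% / 59%. At 34% (170 verified), pelvis could reach 170 × 0.27/(0.76 × 0.70) = 86 cases, 91% / 93%. So the statement that every region falls below 90% at 500 holds at 25% verification, not at every rate.

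A reader might also infer that the primary endpoint is underpowered. The success rule in 8.3.2 is per patient only, and regional sensitivity is reported there with Wilson intervals. The power calculation does not support that inference for the per-patient test against 50%. That test is distinct from the success rule, which requires an observed 70% in two of three readers.

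Finally, 8.2.1 allows the sample size to be adjusted after analysis of the first protocol. This is optional, has no stated rule, and does not correct the present claim. Reading 250 a year as one site's rate does not fit 8.2.2, which refers to the trial.

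**Conclusion.** Both contradictions are in the text, and confidence in them is high: up to 500 patients against 1,500, with study completion at either three years or 48 months; and 20% in each region against 11% for bone. Confidence in the size of the bone shortfall is moderate. At 375 verified and a true sensitivity of 70%, bone power lies between about 54% and 91%, and three of the four conversions fall clearly below 90%. The blanket claim of adequate per-region power is therefore unsupported for bone, rather than shown to be false. A prostate bed shortfall depends on the conversion; pelvis and extrapelvic tissue are adequate at 375. At 500 enrolled and 25% verified, bone power is roughly 16% to 38% and every region is below 90% under these conversions. The consequence is mainly imprecise regional estimates and an unsupported reason for 375 verified instead of 107. This should be fixed.

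**What to change.** - Reconcile 8.2.2 with 3.2, 3.5 and the abstract. State either the accrual rate and period that give 1,500, or the per-region and per-patient power at the number the stated accrual delivers (500, or 750 or 1,000 if accrual runs to 36 or 48 months). Give one study completion date.
- In 8.2.1, replace the blanket per-region claim with power and an expected Wilson interval for each region, from the listed shares. State how shares convert to diseased verified cases, including whether they are PET-positive rates, and state the verification rate, with any different rate for bone. Give a range for both.
- For bone, say that 90% power at 375 verified is not supported under most readings (about 54% to 91%). Do not assert a single value.
- Describe the 75 as reference-standard-positive units (regions or patients) rather than true positives. Show that 107 is 75/0.70 and say what 0.70 stands for.

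The cost is wording in 8.2.1, 8.2.2, 3.5 and the abstract. The 0.05/5 adjustment stays. The stated regional power becomes less favourable, and no extra patients are required unless the sponsor chooses to power bone.

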8.2.2 Accrual estimates

We estimate that roughly 250 patients with prostate cancer will be enrolled in this trial per year. Over a two-year period this will result in up to 500 patients being enrolled in the study.

8.3 Analyses Plans

8.3.1 Analysis Population

Patients with histopathology correlates will be analyzed for the Primary Aim. All remaining patients will be analyzed for the secondary endpoints.

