5.2 Monitoring and Toxicity Management

Each patient receiving Ga-68 PSMA-11 will be evaluable for safety. The safety parameters include physical findings and spontaneous reports of adverse events reported to the investigator by patients.

6 Study Procedures and Observations (Appendix 2)

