7.2 Evaluation of Safety

Analyses will be performed for all patients receiving ⁶⁸Ga-PSMA-11. The study will use the [CTCAE v4.0](#) for reporting of adverse events.

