8.3.3 Analysis of Secondary Endpoints

1. PPVs on a per-patient and per-region-basis of ^{68}Ga -PSMA-11 PET for detection of tumor location confirmed by histopathology/biopsy, clinical and conventional imaging follow-up will be calculated and reported along with the corresponding two-sided 95% confidence intervals. The confidence intervals will be constructed using the Wilson score method. PPV will be reported for each of the three blinded readers independently.
2. Sensitivity and PPVs on a per-patient and per-region basis of ^{68}Ga -PSMA-11 PET for detection of tumor location confirmed by histopathology/biopsy will be summarized in tabular format. Ninety-five percent confidence intervals of sensitivity, specificity, NPV and PPV will be calculated using the Wilson score method. These will be reported for each of the three blinded readers.
3. Detection rates on a per-patient basis of ^{68}Ga -PSMA-11 PET stratified by PSA value (0.2 - <0.5, 0.5 - <1.0, 1.0 - <2.0, 2.0 - <5.0, ≥ 5.0) will be summarized in tabular format and compared between PSA strata using chi-square analysis. Detection rate will also be stratified by history of prostatectomy, radiation or both; as well as by whether the patient is on androgen deprivation therapy (ADT). We will use local interpretations for this analysis.
 - a. Detection rate is defined as number of patients with PSMA positive disease, independent of pathology, imaging or clinical follow-up. A detection rate will be reported for each reader independently stratified by PSA.
4. The impact of ^{68}Ga -PSMA-11 PET on clinical management in BCR patients will be evaluated using descriptive statistics.
5. Inter-reader reproducibility for positivity at the patient level and region level will be reported using the Fleiss' Kappa test for multiple readers. We will use the three blinded reads for this analysis.
6. Safety will be reported descriptively as rates of patient reported adverse events. Additionally, adverse events will be characterized and quantified by CTCAE 4.03.

9 Study Management

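### Section 8.3.1 limits the secondary endpoints to patients without histopathology, which conflicts with the endpoint definitions: the biopsy-confirmed endpoint would have no patients and the detection rate would probably be biased downward

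*Combined protocol and SAP*

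**What the plan says.** Section 8.3.1 consists of two sentences. The first is "Patients with histopathology correlates will be analyzed for the Primary Aim"; the second is "All remaining patients will be analyzed for the secondary endpoints". It is the only section headed as defining analysis populations.

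Section 8.3.3 lists six secondary analyses. Three bear directly on this rule:

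- Item 1 is PPV against the composite reference standard, which includes histopathology.
- Item 2 is sensitivity and PPV "for detection of tumor location confirmed by histopathology/biopsy will be summarized in tabular format".
- Item 3 is the detection rate, with the definition: "Detection rate is defined as number of patients with PSMA positive disease, independent of pathology, imaging or clinical follow-up".

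Safety is item 6, with no population named there. Other sections do name one. Section 5.2 says "Each patient receiving Ga-68 PSMA-11 will be evaluable for safety", 7.1 makes all patients evaluable for toxicity, and 7.2 says "Analyses will be performed for all patients receiving" the agent.

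On how often biopsy happens and in whom, 8.2.1 reports that in the earlier cohort "19% of patients underwent biopsy after a positive PSMA PET imaging", with no true or false negatives on biopsy. It expects the biopsy rate to fall in this study.

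**The concern.** The word for the second group in 8.3.1 makes it the complement of the first. A patient with pathology is therefore outside every secondary analysis. This matters in three ways.

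- Item 2 can be computed only in patients with pathology, and the rule sends all of them elsewhere.
- Composite PPV keeps only cases verified by imaging or clinical follow-up, although 8.3.2(d) ranks pathology above those.
- Detection rate becomes conditional on not having been biopsied. If biopsy tends to follow a positive scan, exclusion depends on the test result, and positives leave the numerator and denominator together.

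An analyst must either follow the text and lose a listed endpoint, or choose populations later, possibly with results in view. Section 1.1 says the data are to be pooled for a final NDA submission, so the populations should be fixed beforehand.

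**Working it through.** **Endpoint against population**

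| Secondary analysis | Who is needed by its definition | Who is left under 8.3.1 |
|---|---|---|
| Item 1, composite PPV | PET-positive patients with an evaluable reference standard, pathology included | only those verified by imaging or clinical follow-up |
| Item 2, biopsy-confirmed sensitivity and PPV | patients with histopathology | none (n = 0) |
| Item 3, detection rate | scanned patients, whatever their pathology | scanned patients without pathology |
| Item 6, safety | every dosed patient (5.2, 7.1, 7.2) | dosed patients without pathology |

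The result for item 2 needs no assumed figure. No other section names a population for items 2 or 3.

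**Detection rate: inputs**

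- PET-negative share: 24% (8.2.1), so P = 1 - 0.24 = 0.76 PET-positive. The listed positive shares add to 15 + 27 + 24 + 11 = 77%.
- Biopsy rate: 19% in the earlier cohort (8.2.1). The text can be read as 19% of all patients or 19% of PET-positive patients.
- Enrolment: 1,500 (3.2).
- PET-positive share among biopsied men, f: 100% on the earlier cohort's experience; lower values are assumptions.

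The plan states no expected detection rate; 76% is the figure implied by its disease distribution.

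**Formula.** With b the biopsied share of all patients, the detection rate in the remaining patients is (P - b × f) / (1 - b).

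| Scenario | Calculation | Rate | Bias (points) |
|---|---|---|---|
| All scanned patients | 1 - 0.24 | 76.0% | 0 |
| 19% of all biopsied, f = 100% | (0.76 - 0.19) / 0.81 | 70.4% | -5.6 |
| 19% of PET-positives biopsied (b = 0.19 × 0.76 = 0.144), f = 100% | (0.76 - 0.144) / 0.856 | 71.9% | -4.1 |
| 10% of all biopsied (assumed), f = 100% | (0.76 - 0.10) / 0.90 | 73.3% | -2.7 |
| 5% of all biopsied (assumed), f = 100% | (0.76 - 0.05) / 0.95 | 74.7% | -1.3 |
| 19% of all biopsied, f = 90% (assumed) | (0.76 - 0.171) / 0.81 | 72.7% | -3.3 |
| 19% of all biopsied, f = 80% (assumed) | (0.76 - 0.152) / 0.81 | 75.1% | -0.9 |

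Starting from 77%, the two scenarios based on 19% and f = 100% give 71.6% and 73.1%, a bias of -5.4 and -3.9 points. The bias is downward whenever f exceeds 76%, and vanishes at f = 76%. These scenarios relax one assumption at a time. Relaxing both, with b = 5% and f = 80%, gives (0.76 - 0.04) / 0.95 = 75.8%, a bias of only -0.2.

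**Numbers of patients.** At the earlier biopsy rate, 0.19 × 1,500 = 285 patients, or 0.19 × 0.76 × 1,500 = 217, would have histopathology. These are the patients on whom item 2 should rest.

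**The first sentence of 8.3.1.** Section 8.2.1 combines imaging and biopsy follow-up in the primary aim and asks for 75 / 0.20 = 375 such patients, and 8.3.2 uses the same composite. A Primary Aim limited to histopathology contradicts both, and 217 to 285 falls short of 375.

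**The case against.** The strongest reply is that 8.3.1 is loose wording and that the specific endpoint definitions govern. An analyst who reads 8.3.3 would not compute item 2 on nobody, nor drop biopsied men from a rate defined without regard to pathology. That is probably the intent. But 8.3.1 states a rule rather than leaving a gap, and nothing in the documents says which text prevails.

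Three stronger readings might be inferred, and the documents do not support them.

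- *Safety omits the biopsied patients.* Sections 5.2, 7.1 and 7.2 each include every dosed patient, so all 1,500 stay in under those sections. What stands is a contradiction to reconcile.
- *Every excluded man is PET-positive.* That was the earlier cohort's experience. This protocol defines pathology-based false-negative and true-negative results for PET-negative lesions (8.3.2(c) and (d)), and it admits pathology from the 60 days before the scan, which the scan cannot have prompted. Predominantly PET-positive is as far as the text goes.
- *The bias is 4 to 6 points.* That requires the biopsy rate to stay at 19% and all biopsied men to be PET-positive. Section 8.2.1 expects the rate to fall, so 4 to 6 points is the upper end.

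**Conclusion.** Section 8.3.1 is wrong as written and should be replaced. Followed literally, it leaves the biopsy-confirmed secondary endpoint with no patients, takes the pathology-verified cases out of composite PPV, and makes the detection rate depend on the absence of pathology, against its own definition. The first two consequences follow from the text alone.

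The size of the detection-rate bias does not. It is about -1 to -6 percentage points over the single-assumption scenarios, and rests on the 76% PET-positive share, the biopsy rate, and the assumption that biopsied men are PET-positive more often than the cohort as a whole. It shrinks as the biopsy rate falls, while item 2 remains empty at any biopsy rate. For safety the conclusion goes no further than a conflict between 8.3.1 and sections 5.2, 7.1 and 7.2.

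**What to change.** Replace both sentences of 8.3.1. Changing only the second would keep a Primary Aim restricted to histopathology. Define four sets, state that a patient may belong to several, and name one set for each endpoint:

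1. All injected patients: safety.
2. All patients with a readable PET: detection rate, inter-reader agreement and management impact.
3. All patients with an evaluable reference standard (pathology, imaging or clinical follow-up, alone or combined, consistent with 8.2.1 and 8.3.2): primary composite sensitivity and composite PPV.
4. The histopathology subset of set 3: biopsy-confirmed sensitivity and PPV (secondary item 2).

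The cost is one paragraph, adopted as an amendment under 9.4. It needs no additional patients, procedures or data.

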8.3.2 Analysis of Primary Endpoints

Sensitivity on a per-patient and per-region-basis of ^{68}Ga -PSMA-11 PET for detection of tumor location confirmed by histopathology/biopsy, clinical and conventional imaging follow-up will be calculated and reported along with the corresponding two-sided 95% confidence intervals. The confidence intervals will be constructed using the Wilson score method. For successful completion of the primary endpoint, two of the three readers will need to have an 70% sensitivity for the detection of disease on a per patient level for the cases that have a) imaging follow-up, b) pathology correlation or c) combination of pathology and imaging follow-up and/or pathology correlation.

^{68}Ga -PSMA-11 PET Results Definition

a) Imaging interpretation ^{68}Ga -PSMA-11 PET:

Local Interpretations: PET images will initially be interpreted by a board certified nuclear medicine physician or a board-certified radiologist experienced in reading PET at the time of the imaging study at the institution that the study is being performed. These interpretations will not be used for final evaluation, and will not be reported as part of the primary or secondary endpoints.

Central Read Logistics: Imaging data will be anonymized and collected at a central site. PET data will be interpreted by three different readers in a random order at separate reading sessions. Cross sectional imaging (CT or MRI) from the ^{68}Ga -PSMA-11 PET will be available for anatomic correlate. The Central readers will be blinded to all other imaging results and all other clinical data.

Reader Positivity and Negativity Definition: Regions defined in Table 1 will be graded for the presence of suspected disease on a two-point scale by each reader (0=Negative or 1=Positive). A region will be judged as positive if at least one lesion in this region is visually positive.

Reader Training: ^{68}Ga -PSMA-11 PET/CT reading training set and guides will be provided and completion of this training will be required for all central review readers. Common pitfalls will be reviewed as part of the reader training.

Criteria for visual interpretation:

Regions of suspected disease will be graded on a two-point scale by each blinded reader (0=Negative or 1= Positive). A region will be judged as positive if at least one lesion in this region is visually positive.

- i) Lymph nodes will be considered positive if the ^{68}Ga -PSMA-11 uptake is focal and greater than blood pool (adjacent or mediastinal blood pool).
 - (1) Lymph nodes will be classified further by region: pelvic, retroperitoneal, thoracic, other. Additionally, pelvic lymph nodes will be subclassified according to their localization as follows: R/L obturator, R/L external iliac, R/L internal iliac and other (total of 7 subgroups). These regions will not be used for evaluation of the primary or secondary endpoints, but for exploratory analysis.
- ii) Visceral lesions will be considered positive if the ^{68}Ga -PSMA-11 uptake is focal and greater than physiologic background activity of the involvement organ or anatomic site.
 - (1) Visceral lesions will be classified further by major organ: lung, liver, other tissue. These regions will not be used for evaluation of the primary or secondary endpoints, but for exploratory analysis.
- iii) Bone lesions will be considered positive if the ^{68}Ga -PSMA-11 uptake is focal and greater than physiologic bone marrow.
 - (1) Bone lesions will be classified by further by region: spine, ribs, pelvis, extremities, skull, sternum, clavicle. These regions will not be used for evaluation of the primary or secondary endpoints, but for exploratory analysis.
- iv) Prostate bed and prostate lesions will be considered positive if the ^{68}Ga -PSMA-11 uptake is focal and greater than physiologic background activity of the involvement organ or anatomic site.

Reference Standard Definition

b) Follow-up Imaging:

All patients will be followed up 3-12 months with conventional imaging (dedicated CT, MRI and/or bone scan). Interpretation of follow-up imaging will be performed by local read. For lesions that are reported in the blinded reads but not reported in the local evaluation of follow-up imaging, the local readers will be informed of the location of the lesions and follow-up will be performed for these additional lesions. Preferably, the follow-up conventional imaging should be the same modality/modalities as the initial staging work-up to allow for reproducible and accurate comparisons.

^{68}Ga -PSMA-11 PET validation based on follow-up imaging:

- i) Lymph nodes will be assessed by change in size. ^{68}Ga -PSMA-11 positive lymph nodes will be considered:
 - (1) True positive:
 - For patients undergoing systemic treatment (alone or in combination with targeted treatment): If on post-treatment follow-up imaging within 3-12 months, lymph nodes seen on CT or MRI decrease by more than 30% in short axis diameter and PSA declines by more than 50%.

- If PSA increases by more than 50% on systemic therapy, then a increase in the size of lesion by more than 20% will be considered a true positive lesion.
- In subjects with localized suspected lymph node(s) receiving targeted treatment without concomitant systemic treatment there are two ways to meet true positive disease:
- If the subject shows a decrease of PSA by greater than 50% after targeted treatment and the lymph node does not enlarge (change in size less than 20% or less than 3 mm increase in short axis diameter) [OR]
 - If on post-treatment follow-up imaging within 3-12 months, lymph nodes seen on CT or MRI decrease by more than 30% in short axis diameter (with a minimum of 3 mm in change in size)
- For untreated patients: If on follow-up imaging within 3-12 months, lymph nodes seen on CT or MRI increase by more than 20% in short axis diameter (with a minimum of 3 mm in change in size).
- (2) False positive:
- For patients undergoing systemic treatment (alone or in combination with targeted treatment): If on post-treatment follow-up imaging within 3-12 months, lymph nodes seen on CT or MRI increase by more than 20% in short axis diameter and PSA decreases by more than 50%.
- In subjects with localized suspected lymph node(s) receiving targeted treatment without concomitant systemic treatment there are two ways to meet false positive disease:
- If the subject does not demonstrate a decrease of PSA by greater than 50% after targeted treatment [OR]
 - If on post-treatment follow-up imaging within 3-12 months, lymph nodes seen on CT or MRI increase by more than 20% in short axis diameter (with a minimum of 3 mm in change in size)
- For untreated patients: If on follow-up imaging within 3-12 months, lymph nodes seen on CT or MRI decrease by more than 30% in short axis diameter (with a minimum of 3 mm in change in size).
- (3) If all regions in a patient/region do not meet criteria for either True positive or False positive disease, then the patient/region will be considered inevaluable for primary endpoint.
- ii) Visceral lesions (non-lymph node soft tissue or organ) will be assessed by change in size. ⁶⁸Ga-PSMA-11 positive visceral lesions will be considered:
- (1) True positive:
- For patients undergoing systemic treatment (alone or in combination with targeted treatment): If on post-treatment follow-up imaging within 3-12

months, lesions seen on CT or MRI decrease by more than 30% in long axis diameter and PSA declines by more than 50%.

- If PSA increases by more than 50% on systemic therapy, then a increase in the size of lesion by more than 20% will be considered a true positive lesion.

- In subjects with localized suspected lesions(s) receiving targeted treatment without concomitant systemic treatment there are two ways to meet true positive disease:

- If the subject demonstrates a decrease of PSA by greater than 50% after targeted treatment [OR]
- If on post-treatment follow-up imaging within 3-12 months, lesions seen on CT or MRI decrease by more than 30% in long axis diameter (with a minimum of 3 mm in change in size)

- For untreated patients: If on follow-up imaging within 3-12 months, lesions seen on CT or MRI increase by more than 20% in long axis diameter (with a minimum of 3 mm in change in size).

(2) False positive:

- For patients undergoing systemic treatment (alone or in combination with targeted treatment): If on post-treatment follow-up imaging within 3-12 months, lesions seen on CT or MRI increase by more than 20% in long axis diameter and PSA decreases by more than 50%.

- In subjects with localized suspected lesions(s) receiving targeted treatment without concomitant systemic treatment there are two ways to meet false positive disease:

- If the subject does not demonstrate a decrease of PSA by greater than 50% after targeted treatment [OR]
- If on post-treatment follow-up imaging within 3-12 months, lesions seen on CT or MRI increase by more than 20% in long axis diameter (with a minimum of 3 mm in change in size)

- For untreated patients: If on follow-up imaging within 3-12 months, lesions seen on CT or MRI decrease by more than 30% in long axis diameter (with a minimum of 3 mm in change in size).

(3) If all regions in a patient/region do not meet criteria for either True positive or False positive disease, then the patient/region will be considered inevaluable for primary endpoint.

iii) ⁶⁸Ga-PSMA-11 positive bone lesions will be considered:

(1) True positive:

- If there was a corresponding positive sclerotic lesion on the CT portion of the ^{68}Ga -PSMA-11 PET or on a separate CT obtained ≤ 30 days before or after the PET/CT in the same location as the PSMA uptake.
- If there is focal uptake seen in the same location as the PSMA uptake on the baseline bone scan performed within one month of ^{68}Ga -PSMA-11 PET.
- If there is a lesion noted in the same location as the PSMA uptake on the initial MRI performed within one month of ^{68}Ga -PSMA-11 PET.
- If within 12 months follow-up CT demonstrates development of sclerosis in the same location as the PSMA uptake.
- If within 12 months follow-up MRI demonstrates a new bone lesion in the same location as the PSMA uptake.
- If within 12 months follow-up bone scan demonstrates new focal uptake in the same location as the PSMA uptake.
- In subjects with localized suspected bone lesion(s) receiving targeted treatment without concomitant systemic treatment:
 - o If the subject demonstrates a decrease of PSA by greater than 50% after targeted treatment.

(2) False positive:

- In subjects with localized suspected bone lesion(s) receiving targeted treatment without concomitant systemic treatment:
 - o If the subject does not demonstrate a decrease of PSA by greater than 50% after targeted treatment with curative intent (ie non-palliative radiation).
- If ^{68}Ga -PSMA-11 positive bone lesions do not meet the criteria for true positive findings, and appropriate correlative and follow-up imaging was acquired.

(3) If bone lesions do not meet criteria for either true positive or false positive disease listed above, then the patient/region will be considered inevaluable for primary endpoint.

iv) ^{68}Ga -PSMA-11 positive prostate bed and prostate lesions will be considered:

(1) True positive:

- For patients undergoing systemic treatment (alone or in combination with targeted treatment): If on post-treatment follow-up imaging within 3-12 months, lesions seen on CT or MRI decrease by more than 30% in long axis diameter
- In subjects with localized suspected lesions(s) receiving targeted treatment without concomitant systemic treatment there are two ways to meet true positive disease:

- If the subject demonstrates a decrease of PSA by greater than 50% after targeted treatment [OR]
- If on post-treatment follow-up imaging within 3-12 months, lesions seen on CT or MRI decrease by more than 30% in long axis diameter (with a minimum of 3 mm in change in size)

- For untreated patients: If on follow-up imaging within 3-12 months, lesions seen on CT or MRI increase by more than 20% in long axis diameter (with a minimum of 3 mm in change in size).

(2) False positive:

- For patients undergoing systemic treatment (alone or in combination with targeted treatment): If on post-treatment follow-up imaging within 3-12 months, lesions seen on CT or MRI increase by more than 20% in long axis diameter and PSA decreases by more than 50%.

- In subjects with localized suspected lesions(s) receiving targeted treatment without concomitant systemic treatment there are two ways to meet false positive disease:

- If the subject does not demonstrate a decrease of PSA by greater than 50% after targeted treatment [OR]
- If on post-treatment follow-up imaging within 3-12 months, lesions seen on CT or MRI increase by more than 20% in long axis diameter (with a minimum of 3 mm in change in size)

- For untreated patients: If on follow-up imaging within 3-12 months, lesions seen on CT or MRI decrease by more than 30% in long axis diameter (with a minimum of 3 mm in change in size).

(3) If the lesion does not meet criteria for either True positive or False positive disease, then the lesion will be considered inevaluable for primary endpoint.

c) Histopathology/Biopsy:

- i) ⁶⁸Ga-PSMA-11 positive findings are aimed to be confirmed by histopathology/biopsy if clinically feasible. Pathology performed 60 days before the PSMA PET will be available for correlation.
- ii) Histopathological procedures and biopsies will be performed as clinically indicated and as per institutional protocol.

(1) Positive Histopathology/Biopsy: Confirmed sites of metastatic or tumor involvement by histopathology/biopsy will be discussed with the responsible physician/surgeon.

- (a) True Positive: lesion is positive on targeted biopsy/surgical sampling and is read as positive on PSMA PET.
- (b) False Negative: lesion is positive on targeted biopsy/surgical sampling and is read as negative on PSMA PET.

- (2) **Negative Biopsy:** Patients with suspected tumor recurrence on ^{68}Ga -PSMA-11 PET with negative histopathology/biopsy will be handled as outlined below:
- (a) Lymph nodes:
- For patients undergoing nodal dissection: Patients will be rescanned with dedicated CT, MRI or a repeat ^{68}Ga -PSMA-11 PET to determine if the suspicious ^{68}Ga -PSMA-11 positive node was removed.
 1. If ^{68}Ga -PSMA-11 positive lymph node is still present, a repeat biopsy can be pursued if clinically feasible and applicable, or follow-up using imaging as described above will be performed.
 2. If the corresponding node was removed, then this will be considered a False Positive.
